- 23. Participation in another investigational study within the greater of 4 weeks or 5 half-lives of an investigational medication prior to screening or during the study.
- 24. Use of strong cytochrome P450 3A4 (CYP3A4) inhibitors (such as, but not limited to clarithromycin, conivaptan, grapefruit juice, indinavir, itraconazole, ketoconazole,

- lopinavir/ritonavir, mibefradil, nefazodone, nelfinavir, posaconazole, saquinavir, telaprevir, telithromycin, voriconazole, or fluconazole) dosed for systemic exposure.
- 25. Use of strong CYP3A4 inducers (such as, but not limited to barbiturates, carbamazepine, efavirenz, glucocorticoids, modafinil, nevirapine, oxcarbazepine, phenobarbital, phenytoin, pioglitazone, rifabutin, rifampin, St. John's Wort, or troglitazone) dosed for systemic exposure.
- 26. Donation of blood > 499 mL of blood or plasma within 56 days of Screening (during a clinical trial or at a blood bank donation) and for 30 days after last dose of study drug.
- 27. Clinically significant medical condition, psychiatric disease, or social condition, as determined by the Investigator, that may unfavorably alter the risk-benefit of study participation, adversely affect study compliance, or confound interpretation of study results.

Investigational product, dosage and mode of administration:

CTP-543 will be dosed orally as tablets at doses of 8 mg, 12 mg, or 4 mg every 12 hours.

Reference therapy, dosage and mode of administration:

Matching placebo will be dosed orally as tablets every 12 hours during Part A, Period 2.

Duration of treatment:

Part A, Period 1: Patients will receive study drug for 24 weeks in the Treatment Period.

Part A, Period 2: Responders from Part A, Period 1 will receive up to 24 weeks of additional treatment with active or placebo.

Part B: Patients will be treated with active drug for 24 weeks.

Patients will be dosed in the study with CTP-543 up to a total of 72 weeks.

Duration of study participation:

Patients will participate in the study for up to approximately 80 weeks if exiting the study after the 4-week Safety Follow-up (4-week Screening, 48-week Treatment Part A, 24-week Treatment Part B, 4 week Safety Follow-up). Upon completion of the 24-week Treatment Period, patients will be eligible to either complete treatment and exit the study following the 4-week Safety Follow-up visit, or enroll into an open-label extension study.

Criteria for evaluation:

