Patients in Part A, Period 2 will stay on their assigned dose for a maximum of 24 weeks or until they meet the criteria for loss of regrowth maintenance (LOM), defined as an absolute SALT score >20. Any patient meeting the LOM criteria at any assessment timepoint during Part A, Period 2 will enter Part B of the study and return to their original CTP-543 treatment from Part A, Period 1 (8 mg BID or 12 mg BID). Patients not meeting the LOM criteria (e.g., their absolute SALT score remains \leq 20) at the end of 24 weeks will have the opportunity to continue receiving treatment in the Open-Label Extension study (CP543.5001) or they will complete treatment at Week 24 and return in 4 weeks for the Post-Treatment Safety Follow-up.

Assessment of treatment response using SALT for efficacy will occur at 4, 8, 12, 16, 20 and 24 weeks. The primary efficacy analysis will be conducted when all patients have completed Week 24 of Part A, Period 2. The study design is depicted below.

Part A: Treatment and Dose Modification Phase

Part B: Re-Treatment Phase

Part B: Re-

Figure 2: CP543.2004 Study Design

LOM: Loss of Maintenance

Part B (Re-Treatment Phase)

Any patient from Part A, Period 2 meeting the LOM criteria (SALT > 20) will enter into Part B of the study and return to their original 8 mg BID or 12 mg BID dose assigned in Part A, Period 1. Patients will stay on their assigned dose for 24 weeks regardless of whether they meet the criteria for Restoration of Regrowth (ROR) or not. ROR is defined as the patient's attainment of an absolute SALT score ≤20. Assessment of treatment response using SALT for efficacy will occur monthly during the 24-week period. Patients will have the opportunity to continue receiving treatment in the Open-Label Extension study (CP543.5001) or they will complete treatment at Week 24 and return in 4 weeks for the Post-Treatment Safety Follow-up.

Safety

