² As Day 1 occurs on the same day as the last visit from Part A, Period 2, eligible subjects for Part B will not have assessments repeated.

³ Also serves as the Early Termination Visit for patient withdrawal in this period or any patient meeting ROR criteria and entering OLE.

⁴ The Safety Follow-Up Visit is intended as an Exit Visit for those patients who do not roll over into an open-label extension and for patients who have been discontinued from the study and completed the Early Termination Visit (Week 24).

⁵ Serum pregnancy test for females of childbearing potential only. Subjects who are surgically sterile or (hysterectomy or bilateral ligation) or post-menopausal (cessation of menses for at least 12 months prior to screening) need not be tested.

⁶ Includes hematology and serum chemistry, fasted.

Includes total cholesterol, low-density lipoprotein, high-density lipoprotein, and triglycerides under fasted conditions.

⁸ Any patient from Part A, Period 2 meeting the LOM criteria will enter into Part B of the study and return to their original 8 mg BID or 12 mg BID dose from Part A, Period 1.

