9.3. Patient Withdrawal Criteria

For all patients, it is the intent that patients who discontinue study medication (at any time) for any reason but do not withdraw consent will continue to be followed for all protocol-planned study visits through the completion of the 24-week treatment period, and will have all endpoints (including efficacy) collected accordingly.

The Investigator, Sponsor, or its designee may decide a patient should discontinue treatment at any time and for any reason. In addition, patients will discontinue randomized treatment if they:

- Experience an intolerable adverse event: such events include, but are not limited to, adverse event ≥ Grade 4*, bone marrow-related events, a ≥ Grade 3* cardiac event (*CTCAE v5.0 criteria);
- Require a medication that is prohibited by the protocol. However, under certain circumstances, and in consultation with the Medical Monitor, short-term use of a prohibited medication may not necessitate withdrawal of treatment when its use is unlikely to unfavorably alter the risk-benefit of subject participation;
- In the opinion of the Investigator, have any medically appropriate reason;
- Become pregnant;
- Have a serious adverse event associated with a SARS-CoV-2 infection;
- The Investigator believes that further treatment is undesirable or the risk-benefit profile has become unfavorable.

Furthermore, dose interruptions lasting more than 21 days may require treatment discontinuation on a case by case basis following consultation with the Medical Monitor.

In addition, patients are free to withdraw from participation in the study at any time, for any reason, and without prejudice. The Investigator must withdraw any patient from the study if the patient withdraws consent and requests to stop participating in the study.

Patients who withdraw or are withdrawn from the study will not be replaced.

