#### 8.1.2. Assessment Time Windows

The visit schedule for all study assessments is provided in Appendix 15.2, by Part. For scheduled visits, there will be no reassignment of the analysis visit based on date. Unscheduled visits and early termination visits will be reassigned based on the analysis windows in the below table and the schedule of events. Assessments in part B will be windowed counting from the part B treatment start date. Assessments may only be re-assigned to visits where they were to be collected per the schedule of events. The latest assessment in a window will be selected as the visit used in summaries, unless otherwise specified. All visits will be included in by-patient data listings.

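### A Part B schedule footnote can be read as letting patients leave for the open-label extension once regrowth is restored, against the 24-week rule; if followed, it would mainly understate Week 24 restoration

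*Protocol*

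**What the plan says.** The design text is clear. Protocol 8.1 (Part B) states: "Patients will stay on their assigned dose for 24 weeks regardless of whether they meet the criteria" for ROR. The Synopsis and SAP section 3 repeat this. On what follows Part B, protocol 8.1 says: "Patients will have the opportunity to continue receiving treatment in the Open-Label Extension study (CP543.5001) or they will complete treatment at Week 24". No ROR condition is attached to the OLE. The Synopsis, under duration of study participation, places the choice between exit and OLE after the treatment period: "Upon completion of the 24-week Treatment Period, patients will be eligible to either complete treatment and exit the study". Protocol 9.3 adds that patients who stop study drug without withdrawing consent "will continue to be followed for all protocol-planned study visits through the completion of the 24-week treatment period".

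The Part B Schedule of Assessments says something different. Footnote 3, attached to the Week 24 (Visit B8) column, reads: "Also serves as the Early Termination Visit for patient withdrawal in this period or any patient meeting ROR criteria and entering OLE". SAP Appendix 15.2 reproduces it.

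The SAP's Part B primary endpoint is SALT ≤20 at Week 24 of re-treatment (SAP 8.2). SAP 8.1.2 handles visits in two ways. On the one hand, "For scheduled visits, there will be no reassignment of the analysis visit based on date". On the other, "Unscheduled visits and early termination visits will be reassigned based on the analysis windows in the below table and the schedule of events". SAP 8.2.1 uses the last observed SALT only for the end of Part A Period 2 and otherwise imputes nothing. SAP 8.2.3 specifies no sensitivity analysis.

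**The concern.** A patient who completes Week 24 does not need an Early Termination Visit. Naming ROR patients who enter the OLE as users of that visit therefore reads naturally as an exit route before Week 24, open only to patients who have already met the endpoint. Sites work from the schedule of assessments, so the footnote is an operative instruction and can be acted on even where the design text disagrees.

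At stake is the answer to the secondary objective: whether returning to the original dose restores regrowth. Any exit under this clause would depend on outcome, and the SAP has no rule for how it counts at Week 24. The Part B disposition categories in SAP 6.1 would not separate such patients from ordinary OLE entrants.

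**Working it through.** The documents give no Part B sample size, ROR rate or exit rate, so there is no plan figure to reproduce. The check has two steps: what the SAP would do with an early exit, and which way the rate would move.

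**Step 1: what happens to the visit.** Part B visits at Weeks 4, 8, 12, 16 and 20 have target days 29, 57, 85, 113 and 141 (7 × week + 1), each ±2 days. The Part B efficacy window for Week 24 in the SAP's analysis-window table is days 166 to 172.

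- *Handled as early termination.* A SALT at one of those visits is assigned to its own week. For example, the Week 20 visit falls on days 139 to 143, inside the window 138 to 144. Days 145 to 165 (165 − 145 + 1 = 21 days) lie in no efficacy window. In every case before day 166 there is no Week 24 value, and nothing is imputed.
- *Recorded as scheduled Visit B8.* The visit is not reassigned by date, so the early SALT counts as Week 24.

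**Step 2: direction.** Let e = share reaching ROR before Week 24; f = share of those who leave; r = share of early ROR patients who would be back above SALT 20 at Week 24 if kept; q = Week 24 ROR rate among the rest.

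- Everyone kept 24 weeks: T = e(1−r) + (1−e)q.
- Week 24 successes still seen after exits: S = e(1−f)(1−r) + (1−e)q.
- Early termination, full denominator (the SAP section 4 default): rate S, shift −ef(1−r). This is never upward.
- Early termination, observed cases (shown because SAP 8.2.2 speaks of observed percentages): rate S/(1−ef). This exceeds T only if q > 1−r, meaning that early responders would do worse at Week 24 than patients who had not responded early.
- Recorded as Visit B8: rate S + ef, shift +efr. This is upward only if some leavers would have relapsed.

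**Illustration, all rates assumed:** e = 0.5, r = 0.1, q = 0.4, so T = 0.45 + 0.20 = 65%.

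| Share leaving, f | Early termination, full denominator | Early termination, observed cases | Recorded as Visit B8 |
|---|---|---|---|
| 1 | 0.20 = 20% (−45 points) | 0.20/0.50 = 40% (−25) | 0.20 + 0.50 = 70% (+5) |
| 0.1 | 0.405 + 0.20 = 60.5% (−4.5) | 0.605/0.95 = 63.7% (−1.3) | 0.605 + 0.05 = 65.5% (+0.5) |
| 0 | 65% (0) | 65% (0) | 65% (0) |

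Over assumed ranges e 0.3 to 0.7, r 0 to 0.2, q 0.2 to 0.4 and f 0.5 to 1, the shifts run from −12 to −70 points (full denominator), −5 to −56 (observed cases) and 0 to +14 (Visit B8). These show direction and sensitivity; they do not predict the result.

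Per patient, one leaver moves a sequence's rate by at most 1/N. Protocol 13.1 plans about 25 patients per Period 2 arm, so N is at most about 25 and one patient is worth up to 1/25 = 4.0 points, or more in a smaller sequence. That bound holds for any single lost or misclassified patient, so it does not measure this clause.

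**The case against.** The strongest reply is that the footnote is not an exit rule. It sits on the Week 24 column and describes what that visit also serves as; footnote 4 likewise ties the Early Termination Visit to Week 24. It may mean only that B8 is the last visit before rollover. Supporting evidence:

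- The design text addresses ROR directly and excludes stopping on it. The Synopsis puts OLE entry after the treatment period.
- Where an outcome does move patients, the tables say so at the relevant cell: Part A footnotes 14 and 15 state the SALT >20 action. The Part B Week 4 to 20 SALT and dispensing cells carry no ROR condition.
- SAP 6.1 has a Period 2 completion category for reaching loss of maintenance and entering Part B. Part B has no matching ROR category.

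All of this stands as evidence that early exit was not intended. It does not rescue the clause. On the harmless reading the ROR condition does nothing, because the OLE is open to Part B patients regardless of ROR. Part A's parallel footnote 4 manages without it, although Part A completers may also enter the OLE.

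It is also fair that the upward and downward shifts are not equally likely. The footnote itself calls the visit an Early Termination Visit, and SAP 8.1.2 windows those by date. Overstatement needs the visit to be entered as scheduled Visit B8 despite a ±2-day visit window.

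A reader might infer that the sponsor planned early exit, that patients left this way, or that the clause survives from an earlier design. The documents support none of these. No text reports an early exit, and the amendment summaries show no earlier early-exit rule.

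**Conclusion.** Footnote 3 is wrong as written, in both documents; severity is minor. It conflicts with the 24-week rule or, read kindly, adds a condition that does nothing.

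If followed, it would remove patients selected on success from the Part B primary endpoint and mainly understate Week 24 ROR. Under the SAP's default denominator, an upward shift arises only if the early visit is kept as scheduled Visit B8 and the patient would later have relapsed. A reader might take the large swings in the illustration as the expected bias. They rest wholly on assumed rates, mostly with half or more of early responders leaving. The true size is unknown, and zero if nobody left early.

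Early SALT values would remain visible in the Week 4 to 20 ROR summaries when they fall in those windows, and in the by-patient SALT listing, but not as true Week 24 results. No hypothesis test is involved, and the Part A co-primary analyses are unaffected.

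**What to change.** In protocol Table 2, footnote 3, delete the clause about patients who meet ROR and enter the OLE, so that the footnote covers withdrawal only, as Part A footnote 4 does. Make the same deletion in SAP Appendix 15.2. Meeting ROR is then no reason to leave before the Week 24 SALT. This does not guarantee a Week 24 SALT for everyone; missed visits, for example those due to COVID-19 under protocol 11.2, remain possible.

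If any patient has already left early on ROR, state in SAP 8.2.1, before final lock, how that patient counts at Week 24 whichever way the visit was recorded, and show the result beside the observed figure.

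The cost is one clause in two copies of one footnote, carried in the next amendment. Protocol 14.4 limits administrative amendments to changes with no effect on patient safety, the scope of the investigation or study quality, so the sponsor should decide the classification and not assume it. No new analysis is needed unless early exits have occurred.

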9. SELECTION AND WITHDRAWAL OF PATIENTS

Patients eligible for enrollment in the study must meet all of the following inclusion criteria and none of the exclusion criteria.

9.1. Patient Inclusion Criteria

- 1. Written informed consent, and authorization for release and use of protected health information.
- 2. Between 18 and 65 years of age, inclusive, at the time of informed consent.
- 3. Definitive diagnosis of alopecia areata with a current episode of scalp hair loss lasting at least 6 months and not exceeding 10 years at the time of Screening. Total disease duration greater than 10 years is permitted.
- 4. At least 50% scalp hair loss, as defined by a SALT score ≥50, at Screening and Baseline.
- 5. If of reproductive age, female participants and female partners of male participants, willing and able to use a medically highly effective form of birth control from at least 4 weeks prior to Baseline until at least 30 days following last dose of study drug. Examples of medically highly effective forms of birth control are:
 - a. Confirmed infertility due to surgical procedure
 - b. Post-menopausal (cessation of menses for at least 12 months prior to screening)
 - c. Infertility of sexual partner or partner of the same sex
 - d. Implants of levonorgestrel in females
 - e. Contraceptive (combined oral, patch, vaginal ring, injectable, implant) in females
 - f. Double-barrier method (any combination of physical and chemical methods)
 - g. Intrauterine device with a failure rate less than 1% per year
- 6. Male participants must:
 - a. Agree to use, with their partners, one of the highly effective contraceptive methods listed in Inclusion Criterion 5, from Baseline until at least 30 days following last dose of study drug.
 - b. Refrain from donating sperm during the study and for at least 30 days after the end of the study.
- 7. Willing to comply with the study visits and requirements of the study protocol.

9.2. Patient Exclusion Criteria

- 1. History or presence of hair transplants.
- 2. Treatment with other medications or agents within 1 month of Baseline or during the study that may affect hair regrowth or immune response, including but not limited to: corticosteroids administered orally, intravenously or intramuscularly, or applied to areas of skin affected by alopecia (intranasal and inhaled corticosteroids are allowed, eye and ear drops containing corticosteroids are also allowed); oral retinoids, oral cyclines (minocin, tetracycline); platelet-rich plasma injections; topical application to affected areas of retinoids, anthralin, squaric acid, diphenylcyclopropenone, or minoxidil.

- 3. Treatment with systemic immunosuppressive medications including but not limited to methotrexate, cyclosporine, azathioprine, chloroquine derivatives, etanercept, JAK inhibitors within 3 months of Screening or during the study.
 - NOTE: Patients previously treated with a Janus Kinase inhibitor more than 3 months prior to Screening may be allowed to enter the study at the discretion of the PI, if their previous treatment with a JAK inhibitor was well tolerated, and subsequent JAK treatment would not be thought to put the subject at risk. Consultation with the Medical Monitor may be warranted should questions arise with regard to prior tolerability.
- 4. Treatment with biologics (e.g., adalimumab, atlizumab, canakinumab, certolizumab, fontolizumab, golimumab, infliximab, mepolizumab, rituximab, secukinumab, tocilizumab, ustekinumab) within 6 months of Screening or during the study.
- 5. Active scalp inflammation, psoriasis, or seborrheic dermatitis requiring topical treatment to the scalp, significant trauma to the scalp, or other scalp condition that may interfere with the SALT assessment, or untreated actinic keratosis anywhere on the body at Screening and/or Baseline.
- 6. Known history of moderate to severe androgenic alopecia or female pattern hair loss prior to alopecia areata.
- 7. Unwilling to maintain a consistent hair style, including shampoo and hair products (including hair dye, process, and timing to hair appointments), and to refrain from weaves or extensions throughout the course of the study, or shaving of scalp hair for 2 weeks preceding a SALT assessment.
- 8. Use of adhesive wigs, other than banded perimeter wigs, during the study.
- 9. History of a lymphoproliferative disease or malignancy, other than non-melanoma skin cancer or cervical carcinoma. Patients with 3 or more basal or squamous cell carcinomas diagnosed in the past 2 years are excluded.
- 10. History of solid organ or hematological transplantation.
- 11. Fever, inflammation, or systemic signs of illness suggestive of systemic or invasive infection or a positive SARS-CoV-2 test result within 2 weeks prior to Baseline.
- 12. Abnormal levels of thyroid stimulating hormone at Screening, defined as <0.9 x the lower limit of normal (LLN) and >1.5 x the upper limit of normal (ULN).
- 13. Screening labs outside the normal range for parameters associated with potential risk for treatment under investigation. This will include but is not limited to:
 - a. Platelets $<100 \times 10^9/L$ or $>600 \times 10^9/L$
 - b. Absolute neutrophil count $\leq 1.5 \times 10^9/L$
 - c. Hemoglobin levels \leq 10.5 g/dL for females, or hemoglobin levels \leq 12.0 g/dL for males
- 14. Screening blood level of hemoglobin A1c ≥7.5% (58 mmol/mol, 9.3 mmol/L).
- 15. Abnormal liver function at Screening, defined as $\ge 2 \times ULN$ of serum alanine transaminase, serum aspartate transaminase, and serum alkaline phosphatase, or $\ge 1.5 \times ULN$ total bilirubin (unless isolated Gilbert's syndrome).

- 16. Abnormal renal function (estimated glomerular filtration rate <60 mL/min/1.73 m² using the CKD-EPI 2009 equation) at Screening.
- 17. Patient has positive results for hepatitis B surface antigens (HBsAg), antibodies to hepatitis B core antigens (anti-HBc), or hepatitis C virus (HCV) at Screening, or known history of human immunodeficiency virus infection. Subjects who test positive for HCV but who are in remission (sustained virologic response as evidenced by undetectable HCV RNA level using a sensitive assay≥ 12 weeks after completion of HCV therapy) are allowed inclusion in the study.
- 18. Vaccination with a live attenuated vaccine during the study or up to 6 weeks prior to randomization.
- 19. History of previous active disease due to *M. tuberculosis* (TB) without documentation of successful treatment; OR, patient has a positive result from a Tuberculin Skin Test (TST) or a QuantiFERON-TB Gold (QFT) test performed at Screening.
 - NOTE: If the patient has a positive QFT result at Screening and: (1) has no history of successful treatment for either active disease or latent infection due to M. tuberculosis, or (2) currently resides in an area with low prevalence of tuberculosis, or (3) has no lifetime history of occupational or household exposure to person(s) with tuberculosis, then the initial Screening QFT result may be a false-positive. In this instance, a second Screening test for latent TB infection should be obtained either: (1) a repeat QFT test or (2) a Tuberculin Skin Test (TST). The repeat QFT test must be negative or the TST should show <15mm induration (considered negative TST) before being considered eligible for the study.
- 20. History of prolonged QT syndrome or a Screening QTc interval with Fridericia's correction (QTcF) > 450 msec for males or QTcF > 470 msec for females.
- 21. History of alcohol, medication, or illicit drug abuse within 1 year before the first dose of study drug.
- 22. Females who are nursing, pregnant, or planning to become pregnant while in the study, and for 30 days after last dose of study drug.
- 23. Participation in another investigational study within the greater of 4 weeks or 5 half-lives of an investigational medication prior to screening or during the study.
- 24. Use of strong cytochrome P450 3A4 (CYP3A4) inhibitors (such as, but not limited to clarithromycin, conivaptan, grapefruit juice, indinavir, itraconazole, ketoconazole, lopinavir/ritonavir, mibefradil, nefazodone, nelfinavir, posaconazole, saquinavir, telaprevir, telithromycin, voriconazole, or fluconazole) dosed for systemic exposure.
- 25. Use of strong CYP3A4 inducers (such as, but not limited to barbiturates, carbamazepine, efavirenz, glucocorticoids, modafinil, nevirapine, oxcarbazepine, phenobarbital, phenytoin, pioglitazone, rifabutin, rifampin, St. John's Wort, or troglitazone) dosed for systemic exposure.
- 26. Donation of blood > 499 mL of blood or plasma within 56 days of Screening (during a clinical trial or at a blood bank donation) and for 30 days after last dose of study drug.
- 27. Clinically significant medical condition, psychiatric disease, or social condition, as determined by the Investigator, that may unfavorably alter the risk-benefit of study

participation, adversely affect study compliance, or confound interpretation of study results

